To date, there remains a paucity of robust evidence regarding the risk factors, incidence, and outcomes in major abdominal surgery. Firstly, there is a lack of contemporary data on cardiovascular outcomes with the recent consensus definitions for the Standardized Endpoints in Perioperative Medicine (StEP) initiative.¹³ New data assessing rates of these new composite cardiovascular endpoints would provide benchmarking data for future randomised controlled trials. Secondly, there are limited European guidelines regarding the prevention (i.e. perioperative beta-blocker therapy) and/or management of cardiovascular complications. Royal College of Anaesthetists Guidelines for the Provision of Anaesthesia Services (GPAS) provide a number of risk reduction strategies and standards within the pre-, intra- and post-operative periods. In addition, relevant Enhanced Recovery After Surgery (ERAS) protocols exist to minimise postoperative cardiovascular complication.²¹ Further, risk modification (i.e. anaemia, frailty) on postoperative cardiovascular complications remain an area of uncertainty.²²

CASCADE (CArdiovaSCular outcomes after major abDominal surgEry) aims to increase our understanding of variability and adherence to risk reduction measures for postoperative cardiovascular complications following major abdominal surgery through an international, multicentre study across Europe.

Audit Standards

* *Relevant audit standards from selected American College of Cardiology (ACC) / American Heart Association (AHA), Enhanced Recovery after Surgery, National Institute of Clinical Excellence guidelines*

Pre-operative Standards	
1. Weight and body mass index should be recorded.	
Royal College of Anaesthetists: Guidelines for the Provision of Anaesthesia Services 2021²³
 
 • Pre-operative Assessment and Preparation Recommendation 12.44: Medical records should include the patient's weight and body mass index (BMI)

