 - Staged with a planned return for reoperation (such as but not limited to damage control laparotomy or burns surgery) OR
 - Change in operative plan such that during the first procedure it is determined that a reoperation is necessary, even if the patient was enrolled preoperatively
- **Return to theatre:** Each individual patient should only be included in the study *once*. Patients returning to theatre due to complications following earlier surgery can be included, as long as their indexed procedure has not already been included in the CASCADE audit.

You should collect data on consecutive patients operated at your centre during the data collection period. This means that all eligible patients should be included.

Strategies to identify consecutive eligible patients could include:

- *Daily review of elective theatre lists.*
- *Daily review of handover sheets/ emergency admission and ward lists.*
- *Daily review of theatre logbooks (both elective and emergency).*

6. Covariates:

Data will be collected on audit standards and confounding factors for risk-adjusted analyses. These include age, sex, ethnicity, body mass index, American Society of Anaesthesiologists (ASA) grade, relevant comorbidities, smoking status, anticoagulant or antiplatelet use, preoperative blood test values, and preoperative anaemia management. Variables including operative urgency, operative procedure, operative contamination, use of tranexamic acid, intraoperative blood transfusions used, haemoglobin level at transfusion, duration of procedure and post-operative iron therapy will also be collected. Without appropriately adjusting for risk factors, it is likely that any findings would be biased and unable to be appropriately analysed on a national scale. A full list of required data fields is available in **Appendix B**, and on the REDCap database.

7. Outcome Measures and Follow-up:

Primary outcome measure:

- Rates of compliance to pre-, intra-, and postoperative audit standards in reducing risk of postoperative cardiovascular complication.

Secondary outcome measures:

- Incidence of postoperative cardiovascular complications within 30-days of surgery according to the Standardized Endpoints for Perioperative Medicine (StEP) cardiovascular.¹³ (see **Appendix D: Definitions of Key Outcomes**).
- 30-day postoperative blood transfusion rates
- 30-day complication rates defined according to the Clavien-Dindo classification (see **Appendix D: Definitions of Key Outcomes**)

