Appendix B: Data Dictionary

Pre-operative Data Fields	Required data (definition / comment)	Suggested source(s)
1. Patient age	Years (whole years at the time of operation)	– Clinical letters / notes
2. Patient sex	Male / Female	– Clinical letters / notes
3. Patient body mass index (BMI)	kg/m² (record to two decimal places)	– Drug charts – Clinical letters / notes
4. Patient ASA grade	Grade I-V (Full ASA classification available at: https://www.asahq.org/resources/clinical-information/asa-physical-status-classification-system)	– Anaesthetic notes
5. Smoking status	Current (≤6 weeks, >6 weeks), Previous, Never	– Admissions clerking – Clinical notes
6. Clinical Frailty scale	1-3 / 4-6 / 7-9 (Full Clinical frailty scale available at: https://www.dal.ca/sites/gmr/our-tools/clinical-frailty-scale.html)	– Admissions clerking – Clinical notes
7. History of cardiovascular disease	Yes (myocardial infarction, angina, congestive cardiac failure, TIA/stroke, hypertension, peripheral vascular disease, atrial fibrillation, VTE, pulmonary embolism) / No If congestive cardiac failure, what is the NYHA: I / II / III / IV	– Admission clerking – Anaesthetic notes – Outpatient letters
8. History of respiratory disease	None / Dyspnoea on exertion or CXR (mild COPD) / Dyspnoea limiting exertion to <1 flight or CXR moderate COPD / Dyspnoea at rest/rate >30 at rest or CXR (fibrosis or consolidation)	
9. History of COPD	Yes / No	
10. History of chronic kidney disease	Yes (I / II / IIIA / IIIB / IV / V) / No	
11. History of liver cirrhosis	Yes / No	
12. History of diabetes mellitus	Yes - Type I / Yes - Type II (diet controlled, tablet controlled, insulin controlled) / No	
13. Active cancer and/or cancer treatment	Yes / No	
14. Inflammatory bowel disease	Yes / No	
15. Previous history of VTE	Yes / No	
16. Management of iron-deficiency anaemia	None / Preoperative iron supplementation / Tranexamic acid / RBC transfusion (If yes: 1, 2, 3, 4, ≥5 units)	
17. Preoperative treatment	Yes (Aspirin, ACEi/ARB, β-blocker, α ₂ agonist, rate controlling CCB, DHP CCB) / No If yes, was medication stopped preoperatively? (No / Yes, stopped preop only / Yes, stopped preop & postop)	– Clinical letters / notes PACS software
18. Preoperative therapeutic anticoagulation	Yes (Low Molecular Weight Heparin (LMWH), Warfarin, Direct acting oral anticoagulants (DOACs)) / No	– Clinical letters / notes PACS software

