19. Pre-admission blood tests	Haemoglobin (grams / litre) / Albumin (grams / litre) / Creatinine (ml / min) *Include blood tests taken within the 90 days prior to operation. If multiple blood tests have been taken during this period, record the lowest value. If no pre-admission blood tests are available, please record this as 0.	– Pathology systems
20. Admission blood tests	Haemoglobin (grams / litre) / White cell count (x10 ⁹ / l) / Albumin (grams / litre) / Sodium (mmol/l) / Potassium (mmol/l) / Urea (mmol/l) / Creatinine (ml / min)	– Pathology systems

	*Include the first blood test results from this admission. Only include blood tests taken before surgery	
21. Admission observations	Pulse rate (bpm) / Systolic blood pressure (mmHg) / Glasgow coma scale	–
22. Pre-operative assessment	If elective: Yes (pre-admission anaesthetic assessment clinic) / No. If yes: Did this include pre-operative cardiopulmonary exercise testing (Yes - VO ₂ peak, AT / No). If emergency: Yes (inpatient perioperative or elderly medicine, including physician or nurse specialist) / No	– Clinical letters / notes
23. Preoperative investigations	None / ECG (normal / abnormal) / Echocardiography (LVEF, %) / Coronary angiography	–
Abbreviations: ASA = American Society of Anaesthesiologists; Hb = Haemoglobin; LVEF = Left Ventricular Ejection Fraction PACS = Picture Archiving and Communication.		

Intra-operative Data Fields	Required data (definition / comment)	Suggested source(s)
1. Prior Operations	1 / 2 / >2	
2. Operative urgency (NCEPOD Classification of Intervention)	Immediate (Immediate life, limb or organ-saving intervention - resuscitation simultaneous with intervention. Normally within minutes of decision to operate). Urgent (Intervention for acute onset or clinical deterioration of potentially life-threatening conditions, for those conditions that may threaten the survival of limb or organ, for fixation of many fractures and for relief of pain or other distressing symptoms. Normally within hours of decision to operate) Expedited (requiring early treatment where the condition is not an immediate threat to life, limb or organ survival. Normally within days of decision to operate). Elective (Intervention planned in advance of routine admission to hospital).	– Operative note – Admissions clerking
3. Primary indication	Malignant / Benign If malignant: Primary only / nodal metastases / Distant metastases	– Operative note. – Clinical notes. – Theatre records.

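### Audit standard 1 covers documentation of both weight and BMI, but the form collects only a BMI value: weight documentation has no direct measure, and BMI documentation must be inferred from a filled box

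*Protocol*

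**What the plan says.** The Audit Standards table opens its pre-operative list with "Weight and body mass index should be recorded". The recommendation cited beside it is about the content of the medical record and names both measures.

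Section 7 makes compliance the primary outcome: "Rates of compliance to pre-, intra-, and postoperative audit standards in reducing risk of postoperative cardiovascular complication". Section 2 gives the same as the primary aim.

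Section 6 lists body mass index among the confounders for risk-adjusted analysis and, on what is to be collected, says: "A full list of required data fields is available in" Appendix B, and on the REDCap database. In Appendix B, pre-operative item 3 is BMI in kg/m², with the instruction "record to two decimal places" and with drug charts and clinical letters or notes as suggested sources. Appendix A has the matching two-decimal box. Neither appendix has a field for weight, for height, or for whether weight or BMI was found in the record.

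**The concern.** The standard is about documentation and has two parts. The form takes one number, and that number is designed as a risk-adjustment covariate. A covariate needs the value, wherever it came from. A documentation standard needs to know whether the clinical team wrote it down.

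Two things are lost. No separate rate of weight documentation can be reported. The rate for BMI rests on reading a filled box as a documented BMI, and the form does not say whether the value was copied or worked out. The result enters the primary outcome and is to be fed back to departments, so a rate that is too high would tell a centre that it meets a standard it does not meet. How the standard is scored can be left to an analysis plan, but no analysis plan can create a field that was never collected.

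**Working it through.** No figure in the protocol bears on this point, so the check compares the standard with the form and then works through the possible states of a patient's record.

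**Weight of the standard in the primary outcome.** The Audit Standards table lists 5 pre-operative, 1 intra-operative and 3 postoperative standards: 5 + 1 + 3 = 9. This is one of nine.

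**Standard against form.**

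| What standard 1 needs | What Appendices A and B hold |
|---|---|
| Weight in the record: yes or no | No field |
| BMI in the record: yes or no | No field; a BMI value only |
| A way to mark absence | None for BMI |

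Elsewhere the same forms do these things. Use of the WHO checklist, also an audit standard, is a direct yes/no item (Appendix B, intra-operative item 8). Haemoglobin at transfusion has a not-available option (intra-operative item 12). For pre-admission bloods the dictionary says "If no pre-admission blood tests are available, please record this as 0".

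**What a filled box means.** Assume that charted values are found and entered, and that the box is the only evidence used.

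| State of the record | Meets standard 1? | Box if values are only copied | Box if calculation occurs |
|---|---|---|---|
| Weight and BMI charted | Yes | Filled (right) | Filled (right) |
| BMI charted, weight not | No | Filled (wrong) | Filled (wrong) |
| Weight and height charted, BMI not | No | Empty (right) | Filled (wrong) |
| Weight only | No | Empty (right) | Empty (right) |
| Neither weight nor BMI | No | Empty (right) | Empty (right) |

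**Formula.** Let b be the proportion of patients with BMI charted, u the part of b with no weight charted, c the proportion with weight and height charted but no BMI, and k the share of c for whom the collaborator calculates BMI.

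- Filled boxes = b + k·c.
- Excess over true BMI documentation = (b + k·c) − b = k·c. This is 0 if k = 0 and at most c if k = 1.
- True compliance with both parts = b − u, so the excess over the joint standard = (b + k·c) − (b − u) = u + k·c.

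The documents give none of b, u, c or k. Under these assumptions the direction is fixed, because no term is negative. The size is not.

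**The case against.** The strongest reply is that the form is a fair proxy. Appendix B names drug charts and clinical letters or notes as sources, and Section 7 says that source data come from existing records. Read plainly, the BMI is copied, and a copied BMI is direct evidence that BMI was documented. Most of this stands: where values are copied, the BMI part is measured correctly. What remains is that no instruction says copy only, and nothing on the form separates a copied value from a calculated one.

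Three stronger readings are tempting and are not supported.

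- A reader might infer that collaborators do calculate BMI and that compliance is inflated by some stated margin. The protocol is silent on calculation, so any percentage would be invented, and zero is a possible value.
- A reader might infer that the field carries no information on weight. BMI cannot be obtained without a weight, so a charted BMI implies that a weight was known. It does not prove that the weight was charted, which is the u term above.
- A reader might infer that a patient with a weight but no BMI is wrongly marked down. The standard asks for both, so that patient does fail it and an empty box gives the right answer. What is lost is only a separate weight rate.

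It may also be said that the REDCap build could hold further fields. It is not at hand, but Section 6 presents Appendix B as the full list, and the protocol has to be judged on that. Finally, how a blank BMI is treated under the completeness rules is a separate matter, and this point does not depend on it.

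**Conclusion.** The point holds in a limited form. Standard 1 asks about two documented items, and the form measures neither directly. Weight documentation has no measure of its own. BMI documentation is inferred from a filled box, validly if values are copied, and with an upward error of unknown size if some are calculated.

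The conclusion that weight has no direct measure rests only on the text of the standard and the two appendices. The conclusion about overstated BMI documentation rests on a practice that the protocol neither allows nor forbids. The field is an imperfect proxy, and the defect concerns one documentation item among nine standards in a descriptive audit. It is still worth correcting, because the standard is part of the primary outcome and the gap cannot be closed after data collection.

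**What to change.** At item 3 of Appendix B and the matching box in Appendix A, add two items: weight documented before surgery (yes/no) and BMI documented before surgery (yes/no). Score standard 1 on these two, reporting each part and the two together. State that a no is a complete answer, so that non-compliance is not counted as missing data under the Section 11 and Appendix E completeness rules. Keep the BMI value, copied or calculated, for risk adjustment only. The reference to before surgery also ties the items to a pre-operative standard; item 3 at present sets no time limit, whereas the blood-test items do.

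The cost is two extra ticks per patient, read from notes that are already open. Sample size, eligibility and patient care are unchanged. If only one change can be made, an instruction to enter BMI only when it is documented would remove the calculation problem, but it would leave weight unmeasured and would lose covariate values.

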2. Preoperative scoring tools should be used to risk stratify patients	
ERAS for gastrointestinal surgery: consensus statement for anaesthesia practice²⁴
 
 • Preoperative risk scoring: Preoperative scoring tools and functional capacity tests can be used to identify patients at risk of complications and to stratify perioperative risk 
American College of Cardiology (ACC) / American Heart Association (AHA) Clinical Practice Guideline²²
 
 • Preoperative risk scoring: A validated risk-prediction tool can be useful in predicting the risk of perioperative major adverse cardiovascular events in patients undergoing noncardiac surgery
3. Pre-operative Electrocardiogram (ECG)	
American College of Cardiology (ACC) / American Heart Association (AHA) Clinical Practice Guideline²²
 
 • Preoperative ECG: Pre-operative ECG is recommended for patients who have risk factor(s) and are scheduled for intermediate- or high-risk surgery.
4. Cardiopulmonary exercise testing for high-risk patients	
Royal College of Anaesthetists: Guidelines for the Provision of Anaesthesia Services 2021²³
 
 • Pre-operative Assessment and Preparation Recommendation 2.2: Cardiopulmonary exercise testing or functional assessment for high-risk patients should be carried out.
5. Preoperative iron supplementation in iron-deficiency anaemia	
National Institute of Clinical Excellence: Blood Transfusion Quality Standard (QS138) 2016
 
 • Iron supplementation: People with iron-deficiency anaemia who are having surgery are offered iron supplementation before and after surgery.

Intra-operative Standards	

1. WHO Surgical Safety Checklist should be used for all procedures.
	
Royal College of Anaesthetists: Guidelines for the Provision of Anaesthesia Services 2021²³
 
 • Pre-operative Assessment and Preparation Recommendation 12.50: The WHO's Surgical Safety Checklist should be used and is fully endorsed by the RCoA as the instrument for promoting team working and patient safety.
Post-operative Standards	

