
1. Early recognition of patients needing specialist postoperative input
	
Royal College of Anaesthetists: Guidelines for the Provision of Anaesthesia Services 2019²⁵
 
 • Provision of Postoperative Care Recommendation 3.23: Mechanisms for the early recognition of patients requiring specialist postoperative input from geriatrician-led services and/or critical care should be developed. These should include patients at risk of or presenting with delirium, multiple medical complications, functional decline or complex discharge planning.

2. Postoperative intravenous iron therapy is indicated in patients with iron deficiency anaemia
	
International consensus statement on Postoperative Anaemia after Major Surgery 2018²⁶
 
 • Postoperative iron therapy: Should postoperative iron therapy be indicated, i.v. formulations are recommended

3. Extended pharmacological VTE prophylaxis is indicated in patients at high VTE risk after major abdominal or pelvic surgery
	
National Institute of Clinical Excellence: Venous thromboembolism in over 16s: reducing the risk of hospital-acquired deep vein thrombosis or pulmonary embolism (NG89) 2018
 
 • Consider extending pharmacological VTE prophylaxis to 28 days postoperatively for people who have had major cancer surgery in the abdomen.

Methods

1. Summary

A prospective, multicentre, study will be delivered by STARSurg Collaborative & EuroSurg Collaborative across Europe. Mini-teams of up to four collaborators (medical students and at least one doctor) per speciality group per data collection period will prospectively collect data over a continuous 14-day period at each participating centre. This will be on consecutive patients undergoing major abdominal surgery, with follow-up to 30 postoperative days. All mini-teams should be supervised by a consultant in surgery.

2. Study Aims:

- **Primary Aim:** To audit compliance to pre-, intra-, and postoperative audit standards in reducing risk of postoperative cardiovascular complication.

- **Secondary Aims**
 - To characterise rates and risk factors associated with postoperative cardiovascular complications following major abdominal surgery in Europe.
 - To explore the association of pre-operative and postoperative anaemia with postoperative cardiovascular complications and short-term outcomes (length of stay, readmission and 30-day mortality).

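### Three of the nine audit standards behind the primary outcome are not properly measured: one has no data field, one is only partly captured, and one has only indirect proxies

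*Protocol*

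**What the plan says.** Section 7 of the Protocol gives the primary outcome as "Rates of compliance to pre-, intra-, and postoperative audit standards in reducing risk of postoperative cardiovascular complication". The Audit Standards tables list five pre-operative, one intra-operative and three post-operative standards. On what is collected, Section 6 says "A full list of required data fields is available in" Appendix B, and also on the REDCap database.

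Three standards matter here.

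- **Pre-operative standard 2:** "Preoperative scoring tools should be used to risk stratify patients".
- **Pre-operative standard 4:** headed "Cardiopulmonary exercise testing for high-risk patients". The recommendation cited beneath the heading is wider: "Cardiopulmonary exercise testing or functional assessment for high-risk patients should be carried out".
- **Post-operative standard 1:** "Early recognition of patients needing specialist postoperative input". The cited recommendation asks services to develop mechanisms for this and names geriatrician-led services and critical care.

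The nearest fields in Appendix B are "Patient ASA grade" and the Clinical Frailty Scale band (pre-operative items 4 and 6), the question "Did this include pre-operative cardiopulmonary exercise testing" within pre-operative item 22, and critical care admission (post-operative item 1).

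**The concern.** A compliance rate needs a field showing, for each eligible patient or centre, whether the standard was met. The Protocol does this elsewhere: use of the WHO checklist is a yes/no item, and a pre-operative ECG is a tick-box. For the three standards above, the field is absent, narrower than the standard, or about something else.

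This matters because the gap is in collection. A statistical analysis plan can choose proxies and denominators, but it cannot recover whether a risk score was used or a functional assessment was done if nobody recorded it. Section 4 also requires each team to present its findings locally. A centre that relies on functional assessment could therefore be told that it failed a standard which the cited recommendation says it met.

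**Working it through.** **Count of standards and fields.** Standards: 5 + 1 + 3 = 9. Numbered items in Appendix B: 23 pre-operative + 12 intra-operative + 15 post-operative = 50. Each of the three standards was compared with all 50 items and with the Appendix A form.

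| Standard | What compliance requires | What is recorded | Result |
|---|---|---|---|
| Pre-op 2 | A scoring tool was used to stratify risk | ASA grade I–V; frailty band in three groups; neither can be entered as not recorded | No field for use |
| Pre-op 4 | Exercise testing or functional assessment in high-risk patients | Exercise testing yes/no with VO2 peak and AT, only if elective and seen in the pre-admission clinic | Partly captured |
| Post-op 1 | A mechanism for early recognition | Critical care admission (planned from theatre, unplanned from theatre, unplanned from ward); for emergencies, pre-operative perioperative or elderly-medicine review | Indirect proxies only |

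**(a) Pre-operative standard 2.** ASA grade and frailty band describe the patient. Neither shows that the clinical team used a tool to stratify risk, and computing a score later from comorbidities and blood results does not show it either. Data collectors are told to complete every field, and periods with more than 5% missing data are excluded (Section 11; Appendix E). If either item were counted as the tool, compliance would approach 100% whatever happened in clinic.

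**(b) Pre-operative standard 4.** Among patients who are asked the item 22 question, let p be true compliance with the cited recommendation and q the share of that compliance met by functional assessment alone. Then

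recorded = p × (1 − q), and the error is −p × q.

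The Protocol gives neither p nor q. Over an assumed grid of p = 0.5, 0.7, 0.9 and q = 0.2, 0.5, 0.8:

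- smallest error: 0.5 × (1 − 0.2) = 0.40, which is 10 points low;
- middle: 0.7 × (1 − 0.5) = 0.35, which is 35 points low;
- largest: 0.9 × (1 − 0.8) = 0.18, which is 72 points low.

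The sign is fixed only among patients who are asked. Across all high-risk patients, let e be the share asked, t the proportion of those with exercise testing, f the further proportion with another functional assessment only, and c the true compliance among those not asked. True overall compliance is e(t + f) + (1 − e)c. If the rate is reported among those asked, it is t, and this exceeds the overall truth when

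(1 − e)(t − c) > e × f.

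Take t = 0.10 (assumed) and c = 0 as a limiting case. With f = 0.10 the condition is 0.10(1 − e) > 0.10e, so e < 0.5. With f = 0.50 it is 0.10(1 − e) > 0.50e, so e < 1/6. Below those shares the reported rate is too high for the whole high-risk group; above them it is too low. If patients not asked are instead counted as non-compliant, the rate is e × t, which cannot exceed the truth.

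**Scale.** The anticipated sample in Section 9 reproduces: 300 centres × 10 patients per week × 2 weeks = 6000. At a true proportion of 0.5, the 95% half-width is 1.96 × √(0.5 × 0.5 / 6000) = 1.27 points, ignoring clustering and using the whole sample rather than the high-risk subset. Sample size does not reduce an error from missing fields.

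**(c) Post-operative standard 1.** The cited recommendation concerns how a service is organised, while every Appendix B item is about a patient. No item records a mechanism or post-operative geriatrician-led input. Planned versus unplanned critical care admission is related but ambiguous: an unplanned transfer from the ward may mean that recognition worked or that it came late.

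**The case against.** The best reply is that the three gaps are unequal. A reader might infer that none of the three standards has a usable field. The documents do not support that. Item 22 records exercise testing exactly as standard 4 is headed; the gap is against the wider recommendation beneath the heading. For post-operative standard 1, critical care admission is not the only related field, since item 22 also records perioperative or elderly-medicine review for emergencies, and the planned/unplanned split carries some information.

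A reader might also infer that compliance with standard 4 is biased downward overall. That does not follow: restricting the rate to elective clinic patients can push it up, and the Protocol fixes neither the denominator nor a scoring rule. Both may sit in an analysis plan that is not shown.

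Three further points are fair. NYHA class and breathlessness items are recorded, although as patient descriptors they do not show that a functional assessment was done. Section 6 also points to REDCap, which cannot be seen here; the natural reading is one list in two places. And the outcome is worded as rates, with no all-or-none composite, so standards can be reported singly and a gap in one does not spoil the others.

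None of this rescues standard 2, or supplies the missing functional-assessment and service-level data.

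**Conclusion.** The point holds, in graded form. Of nine standards, one (risk-score use) has no field, so its compliance cannot be calculated; one (exercise testing or functional assessment) is partly captured; and one (early recognition) has only indirect proxies.

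For standard 4, compliance with the cited recommendation is understated among patients who are asked, to the extent that any were assessed by the other route. The net direction over all high-risk patients is open. The size cannot be taken from the document: the 10 to 72 points above come entirely from assumed inputs. The conclusion rests on Appendix B being the complete field list, as Section 6 describes it. The anticipated 6000 patients and the secondary outcomes are unaffected, and nothing here questions the clinical standards themselves.

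**What to change.** Before collection opens:

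1. Add a patient-level field: *Preoperative risk score documented before surgery: yes (which) / no / not recorded*.
2. Add *Other functional assessment: yes / no* beside exercise testing, and ask both questions at all urgencies.
3. Add one question at site registration on whether a pathway for early recognition exists. Compliance with post-operative standard 1 is then reported as a proportion of centres.

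The cost is two extra patient-level fields, a wider branch for the existing exercise-testing question, and one site-level question. Section 4 already requires evidence of registration before data upload, so the site question has a natural place. Patient care and sample size do not change.

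If the fields cannot be added, remove pre-operative standard 2 and post-operative standard 1 from the primary outcome, and restate standard 4 as exercise testing in elective clinic patients only. That costs only wording, but it leaves 9 − 2 = 7 standards, one of them narrower than the recommendation it cites.
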